4.3 Screen Failures and Registered Participants Who Do Not begin Study Treatment

Notify the DCC immediately if the participant screen fails after registration or if the participant does not start treatment.

For non-COH sites, the reason for screen failure will be documented in the registration coversheet (see [Appendix F](#)) and submitted to the DCC.

Issues that would cause treatment delays should be discussed with the Study Principal Investigator.

4.4 Dose Level Assignment

During the Phase 1 portion, eligible participants will be assigned a dose level ([Section 5.3](#)). Once the recommended phase 2 dose (RP2D) is defined, participants will enroll at the RP2D dose ([Section 5.6](#)).

5.0 TREATMENT PROGRAM

[figure not shown]
5.1 Study Overview

This is a prospective, single-arm, multi-center, open-label phase 1/2 study of pembrolizumab (MK-3475) plus pralatrexate in subjects with relapsed or refractory peripheral T-cell lymphomas (PTCL) that have failed at least one prior line of therapy.

In the phase 1 portion, pembrolizumab will be administered at a constant dose of 200 mg IV and pralatrexate will be dose-escalated (range from 15-30 mg/m² IV). The phase 1 portion will use a modified rolling 6 design allowing 3 patients to be treated and evaluated for dose-limiting toxicity simultaneously, with up to 6 patients per dose level. An MTD and RP2D will be selected based on toxicity and tolerability data.

In the phase 2 portion, pembrolizumab will be administered at a dose of 200 mg IV and pralatrexate at the RP2D selected in the phase 1 portion following the same schedule. The phase 2 portion will use a Gehan two-stage design with advancement to the second stage based on ORR in the first stage.

In both phases, patients will receive up to 24 months of combined pembrolizumab and pralatrexate therapy. In both phases, Vitamin B12, Folic acid and Leucovorin will be administered as indicated in the study calendar and [Section 5.13](#).

Each cycle = 21 days. Maximum duration of protocol therapy is 24 months.

Folic acid and Vitamin B12 supplementation is standard of care for pralatrexate therapy.

Folic acid is given daily during the course of therapy. Vitamin B12 is given every 3 cycles.

¹ Disease staging is performed at screening and every 4 cycles until disease progression or off study. Disease staging will be by either PET/CT (preferred) or CT scan, but, if disease is FDG-avid, will be PET/CT at baseline, Cycle 4 and every 8 cycles thereafter. Refer to [Study calendar](#) and [Section 11.1](#) for details.

² Peripheral blood for correlative studies will be collected on C1D1, C2D1, C4D1, C5D1, and at EOT (refer to [Table 9.3.1](#) for additional details).

³ End of treatment visit.

⁴ Follow-up Phase for patients who have completed treatment without disease progression will include staging every 12 weeks for the first year and every 18 weeks thereafter, until disease progression or off study.

5.2 Treatment Cycle Definition

In the absence of a delay due to toxicity, each treatment cycle lasts 21 days \pm 3 days. Day 1 of a cycle is defined as the administration of pembrolizumab.

5.3 Treatment Plan

For a tabular view of the treatment, monitoring, and follow-up schedule, see study calendar in [Section 10](#).

This is a phase 1/2 study, including a phase 1 dose-escalation portion of the study with 2 dose levels and 1 possible de-escalation dose level, for a total of 3 possible dose levels. The starting dose will be 20 mg/m² of pralatrexate on days 1 and 8 and 200 mg IV of pembrolizumab every 21 days, administered in 21-day cycles. The planned dose levels in the Phase 1 portion of the study are outlined in the table below.

Table 5.3 Dosing regimen and schedule

Dose level	Pembrolizumab (Day1)	Pralatrexate (Days 1 and 8)
-1	200 mg IV	15 mg/m ² IV
1	200 mg IV	20 mg/m ² IV
2	200 mg IV	30 mg/m ² IV

In the phase 2 portion of the study, subjects will receive therapy at the RP2D.

Intrapatient dose escalation is permitted in patients enrolled to dose level 1 if and only if the study proceeds to dose level 2 and dose level 2 is determined to be the RP2D. In that case, once dose level 2 is deemed safe and the study proceeds to the phase 2 portion of the study, patients who were enrolled to dose level 1 and are continuing to receive therapy can escalate to dose level 2 in their subsequent cycle of therapy. Patients must meet the criteria for initiation of subsequent cycles of therapy detailed in [Section 5.4](#) of the protocol.

5.4 Eligibility criteria for initiation of subsequent treatment cycles

Prior to initiation of Cycle 2 or any subsequent cycle, and based on the dose delay/modification guidelines provided in [Section 6.3](#) and [Section 6.4](#), patients will need to meet the following eligibility criteria:

- Mucositis \leq grade 1
- Platelet count \geq 25,000/ μ L
- ANC between 500-1,000/ μ L with no fever, or ANC \geq 1000/ μ L
- AST and ALT \leq 3 ULN OR \leq 5 ULN for subjects with hepatic involvement by lymphoma as the etiology of transaminase elevation
- Total serum bilirubin \leq 1.5 ULN OR Direct bilirubin \leq ULN for subjects with total bilirubin levels $>$ 1.5 ULN, unless has Gilbert's disease or hepatic involvement by lymphoma.
- No ongoing \geq grade 3 pralatrexate-related toxicity
- No \geq grade 2 pneumonitis, diarrhea/colitis, hypophysitis, nephritis/renal dysfunction, or intolerable/persistent immune-related AE
- No \geq grade 3 hyperthyroidism
- No evidence of myocarditis or newly onset type I diabetes mellitus
- No \geq grade 3 hyperglycemia associated with evidence of β -cell failure

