5.5 Definition of Dose-Limiting Toxicity

The dose-limiting toxicity (DLT) observation period will be 2 cycles of therapy, from the start of Cycle 1 through the start of Cycle 3, including any delays (regardless of cause) to start of C3. It will be 42 days if there is no delay. If C3D1 is shorter than 42 days from C1D1, DLT will be evaluated through prior to administration of study therapy on C3D1.

Toxicities will be graded according to the National Cancer Institute Common Terminology Criteria for Adverse Events (CTCAE, Version 5.0) accessible at:

https://ctep.cancer.gov/protocolDevelopment/electronic_applications/ctc.htm#ctc_50

DLT will be defined as one of the following AEs that is **at least possibly related** to study treatment:

Hematologic

- Grade 4 neutropenia lasting > 7 days (despite the use of growth factor support).
- Grade 4 thrombocytopenia lasting > 7 days or requiring platelet transfusion.
- Grade 3 or 4 thrombocytopenia associated with grade 2 or higher bleeding.
- Grade 4 anemia not associated with lymphoma.
- Any Grade 5 AE.

Non-hematologic

- Grade \geq 3 pneumonitis without suspected infectious cause.
- Any \geq grade 3 AE that does not resolve to grade \leq 1 within 7 days with the exception of:
 - Grade \geq 3 asymptomatic laboratory abnormalities, including lipase or amylase, that do not require hospitalization or delay of treatment.
 - Grade 3 nausea or vomiting, that improves to grade \leq 2 within 7 days with supportive measures.
 - Grade 3 fatigue that improves to grade \leq 2 within 14 days with supportive measures.
 - Grade 3 asymptomatic endocrinopathy of any duration.
 - Grade 3 fatigue related to endocrinopathy that resolves within 7 days of hormone-replacement or corticosteroid therapy.
 - Grade 3 inflammatory response attributed to local antitumor response of any duration.
 - Vitiligo or alopecia of any grade and duration.
- Any Grade 5 AE

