5.7 Replacement of Subjects

During the Phase 1 portion of the study, subjects will be replaced for any of the following:

- Missed any doses of pralatrexate during the DLT period (not due to DLT).
- Did not receive the doses of pembrolizumab during the DLT period (not due to DLT).

Subjects who are replaced for missed doses may continue to receive study treatment if there is clear clinical benefit, but will not be included in DLT analysis.

During the Phase 2 portion of the study, subjects who did not receive at least 1 dose of pembrolizumab and 1 dose of pralatrexate, or who did not have a tumor response assessment (except due to progression of disease prior to the first tumor response assessment) will be replaced. If a patient discontinues study treatment prior to the first response assessment due to progressive disease, the treating physician is encouraged to obtain imaging to confirm progression.

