6.2 Dose Delay/ Modification - General instructions

If pembrolizumab administration is held for toxicity, and the toxicity is most likely attributed to pembrolizumab and not attributed to pralatrexate, administration of pralatrexate may continue.

If pralatrexate administration is held for toxicity, and the toxicity is most likely attributed to pralatrexate and not attributed to pembrolizumab, administration of pembrolizumab may continue.

In the event that attribution of a treatment-emergent toxicity is unclear, but is at least possibly related to both study medications, both drugs should be delayed/modified according to the most conservative dose delay criteria. The most conservative dose delay criteria should be observed for any particular AEs called out in the dose delay/modification tables (Tables 6.3, 6.4.1, 6.4.2, or 6.4.3) or according to the general “all other IrAE” guidelines in Table 6.3 for unspecified immune-related AEs or the “all other pralatrexate-related” AE guidelines in Table 6.4.3 for non-immune related AEs.

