6.4 Dose Delay/Modifications Guidelines for Pralatrexate-Associated Adverse Events

Pralatrexate dose modifications will be allowed according to the criteria outlined in Table 6.4.1, Table 6.4.2, and Table 6.4.3.

Exceptions:

- For patients who develop severe renal impairment (eGFR or CrCl 15 to < 30 mL/min/1.73m²) while on treatment with pralatrexate at the 30 mg/m² dose level, the dose of pralatrexate upon recovery will be reduced to 15 mg/m².
- For patients who develop severe renal impairment (eGFR or CrCl 15 to < 30 mL/min/1.73m²) while on treatment with pralatrexate at the 20 mg/m² dose level or lower, pralatrexate will be permanently discontinued.

Treatment may be delayed to allow sufficient time for recovery. Patients whose treatment is delayed because of pralatrexate-related toxicity should be evaluated at weekly intervals (or less) until adequate recovery has occurred. A patient who has not received pralatrexate for more than 28 days since last study drug administration should be discontinued from further pralatrexate treatment. Any patient who requires a pralatrexate dose modification due to toxicity should continue to receive the modified regimen for the remainder of the study unless agreed otherwise with the overall study PI or their designee. For patients who require a pralatrexate dose reduction, for any reason, leucovorin should continue to be administered at the specified dose and schedule. For patients who require doses of pralatrexate to be omitted due to mucositis (Table 6.4.1), leucovorin dosing should continue per protocol. For patients who require doses of pralatrexate be omitted for an adverse event other than mucositis or stomatitis (Table 6.4.2 and Table 6.4.3), leucovorin treatment should be stopped until the patient resumes pralatrexate treatment. Safety assessment and routine clinical care should be followed at all times.

Table 6.4.1 Dose Modifications for Mucositis, based on NCI CTCAE Version 5.0

Mucositis Grade on Day of Treatment	Action	Dose Upon Recovery to ≤Grade 1
Grade 2	Omit pralatrexate dose	Continue prior pralatrexate dose
Grade 2 recurrence	Omit pralatrexate dose	Reduce pralatrexate by one dose level (e.g. should be lowered to 20 mg/m ² if receiving 30 mg/m ² , 15 mg/m ² if receiving 20 mg/m ²)
Grade 3	Omit pralatrexate dose Hold pembrolizumab	Reduce pralatrexate by one dose level Resume pembrolizumab

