Grade 4	Permanently discontinue pralatrexate Hold pembrolizumab	If not probably or definitely related to pembrolizumab, pembrolizumab resumption can be considered in discussion with Study PI

Table 6.4.2 Dose Modifications for Hematologic Toxicities

Blood Count on Day of Treatment	Duration of Toxicity	Action	Dose Upon Restart
Platelet ≤25,000/µL	1 week	Omit pralatrexate dose Hold pembrolizumab	Continue prior pralatrexate dose Resume pembrolizumab
	2 weeks	Omit pralatrexate dose Hold pembrolizumab	reduce pralatrexate by one dose level Resume pembrolizumab
	3 weeks	Permanently stop pralatrexate Hold pembrolizumab	Pembrolizumab resumption can be considered in discussion with Study PI
ANC 500-1,000/µL with fever OR ANC <500/µL	1 week	Omit pralatrexate dose, give GCSF support Hold pembrolizumab	Continue prior pralatrexate dose with GCSF support Resume pembrolizumab
	2 weeks or recurrence	Omit pralatrexate dose, give GCSF support Hold pembrolizumab	reduce pralatrexate by one dose level with GCSF support Resume pembrolizumab
	3 weeks or 2 nd recurrence	Permanently stop pralatrexate Hold pembrolizumab	Pembrolizumab resumption can be considered in discussion with Study PI

ANC= absolute neutrophil count, GCSF=granulocyte colony stimulating factor, GMCSF= granulocyte macrophage colony stimulating factor.

Table 6.4.3 Dose Modifications for all Other Pralatrexate-Related Toxicities

Toxicity Grade On Day of Treatment	Action	Dose Upon Recovery to ≤Grade 1
Grade 3	Omit pralatrexate dose	reduce pralatrexate by one dose level
Grade 4	Permanently stop pralatrexate therapy	---

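### For grade 2 mucositis on Day 1 of a cycle, Section 5.4 stops the cycle while Table 6.4.1 omits only pralatrexate; at Cycle 2 Day 1 this decides whether a Phase 1 patient stays evaluable for DLT

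*Combined protocol and SAP*

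**What the plan says.** Section 5.4 covers the start of Cycle 2 and every later cycle: "patients will need to meet the following eligibility criteria". The list includes mucositis of grade 1 or less and no ongoing pralatrexate-related toxicity of grade 3 or higher. It has no provision for starting a cycle with one agent. The section describes itself as based on Sections 6.3 and 6.4.

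Table 6.4.1 gives the action for grade 2 mucositis on the day of treatment as "Omit pralatrexate dose". A pembrolizumab hold is first listed at grade 3. Table 6.4.3, for other pralatrexate-related toxicity, omits pralatrexate at grade 3 and stops it permanently at grade 4. It lists no pembrolizumab hold.

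Section 6.2 says that when pralatrexate is held for a toxicity most likely "attributed to pralatrexate and not attributed to pembrolizumab, administration of pembrolizumab may continue". Section 5.10 likewise allows monotherapy when one agent is delayed. Section 5.2 defines Day 1 of a cycle as the pembrolizumab administration.

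The DLT window in Section 5.5 runs from the start of Cycle 1 to the start of Cycle 3, "including any delays (regardless of cause) to start of C3". Section 5.7 replaces a Phase 1 patient for this reason: "Missed any doses of pralatrexate during the DLT period (not due to DLT". A replaced patient is left out of the DLT analysis.

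**The concern.** Two written rules apply to the same finding on the same day, and they lead to different actions. One delays both drugs. The other gives pembrolizumab, starts the cycle and drops a pralatrexate dose. Section 6.4 also says that treatment may be delayed for recovery, but it does not say when to delay and when to omit.

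In Phase 1 the choice affects the data as well as the treatment. Grade 2 mucositis is not a DLT, because non-hematologic DLTs in Section 5.5 begin at grade 3. A patient with it on Cycle 2 Day 1 is kept in the DLT denominator under one rule and removed under the other. The MTD is set on 6 evaluable patients per dose level, so each inclusion matters. The event is foreseeable: Section 2.3 calls mucositis the most frequent and treatment-limiting adverse event with pralatrexate.

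**Working it through.** The plan gives no figure on this point to reproduce, apart from the window length: 2 cycles × 21 days = 42 days, as Section 5.5 states. The check is a comparison of the rules, followed by one illustration.

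**1. The rules on Day 1 of Cycle 2 or later**

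| Finding on Day 1 | Section 5.4 | Tables, with 6.2, 5.10 and 5.2 |
|---|---|---|
| Grade 2 mucositis | Cycle does not start | Pralatrexate omitted; pembrolizumab may be given, which starts the cycle |
| Other ongoing grade 3-4 pralatrexate-related toxicity | Cycle does not start | Pralatrexate omitted (grade 3) or stopped (grade 4); no pembrolizumab hold listed |
| Other new grade 2 pralatrexate-related toxicity | Cycle may start | No row in Table 6.4.3, so no action: no conflict |
| Low ANC | Same thresholds | Same thresholds (Table 6.4.2): no conflict |
| Platelets | 25,000/µL or more passes | 25,000/µL or less holds both drugs: overlap only at exactly 25,000 |

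**2. The pralatrexate doses in the DLT window**

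The window holds 2 cycles × 2 doses = 4 pralatrexate doses. For grade 2 mucositis that is not a DLT:

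- Cycle 1 Day 1: Section 5.4 does not apply, since it begins with Cycle 2.
- Cycle 1 Day 8 and Cycle 2 Day 8: Section 5.4 does not govern Day 8. An omitted dose leads to replacement under Section 5.7 on either reading.
- Cycle 2 Day 1: under 5.4 the cycle is late, all 4 doses can still be given, the window exceeds 42 days and the patient is evaluable. Under Table 6.4.1, 4 − 1 = 3 doses are given and the patient is replaced.
- Cycle 3 Day 1 closes the window and is not one of the four doses. Under 5.4 a delay lengthens the window; under the tables the window closes when pembrolizumab is given. No dose inside the window is missed.

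So the missed-dose consequence concerns 1 dose of 4. For the grade 3-4 conflict it is weaker still: if the event meets the DLT definition, the patient counts whatever happens to the dose.

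**3. How often the event might occur**

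Section 2.3 reports mucositis with single-agent pralatrexate in about 70% of patients (grade 1 or 2 in 50%, grade 3 or 4 in 21%), generally early in the first cycle. It gives no rate for grade 2 alone and none for its presence at the start of Cycle 2. Let q be the share of patients with grade 2 mucositis on Cycle 2 Day 1; every value is an assumption. The chance that at least one of 6 patients has the event is 1 − (1 − q)^6:

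- q = 2%: 1 − 0.98^6 = 11%
- q = 5%: 1 − 0.95^6 = 26%
- q = 10%: 1 − 0.90^6 = 47%
- q = 25%: 1 − 0.75^6 = 82%

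**The case against.** The strongest reply is that the texts can be read together. Section 5.4 says it is based on 6.3 and 6.4, and 6.4 permits delay, so 5.4 could be the gate for Day 1 and the omit rule could be meant for Day 8. That is workable, but nothing states it. Table 6.4.1 applies to the day of treatment without limiting it to Day 8, and no section gives an order of precedence. The most-conservative rule in 6.2 does not settle it either, because it applies only when attribution is unclear.

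Other parts of the reply stand and limit the point:

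- The event may be uncommon. Day 22 is 14 days after the Day 8 dose, and Section 5.13.2.1 gives leucovorin after every pralatrexate dose. Section 2.4 reports complete resolution by Day 7 in 16 of 17 interventions with reactive leucovorin. This is why the range above starts at 2%.
- Most of the removal of patients with sub-DLT toxicity comes from Section 5.7 itself and would remain after 5.4 is reconciled.
- Section 5.6 lets dose reductions in later cycles inform the RP2D, so intolerance below the DLT threshold is not wholly lost.

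A reader might also infer that ongoing grade 2 toxicity of other kinds is allowed by 5.4 and barred by Table 6.4.3. The documents do not support this. The table has no grade 2 row. Its grade 1 threshold applies only after an omission for grade 3, and only to restarting pralatrexate; a patient improving to grade 2 can start the cycle with pralatrexate still off and satisfy both texts.

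**Conclusion.** The contradiction is real and narrow. It covers grade 2 mucositis on Day 1 of Cycle 2 or later and, similarly, other ongoing grade 3-4 pralatrexate-related toxicity. Its effect on DLT evaluability through a missed dose arises at Cycle 2 Day 1 only; at Cycle 3 Day 1 it changes the window length.

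The 11-82% range rests on an assumed event rate of 2-25% and on independence between patients. A reader might take it as the chance that a patient is handled inconsistently. It is only the chance that the event occurs in at least one of six; inconsistent handling also requires sites to choose different readings, and the documents give no basis for putting a probability on that. A reader might also infer that the MTD would be biased in a known direction. Nothing in the documents establishes that, and no effect on the MTD decision is quantified here. The point should be corrected because two stated rules give different denominators for a primary endpoint and the correction is cheap.

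**What to change.** Reconcile Section 5.4 with Sections 6.2 and 5.10 and Tables 6.4.1 and 6.4.3. State which governs on Day 1 of a cycle and, for each grade of toxicity, whether the cycle is delayed or one agent is omitted. In Section 5.7, define how a delayed pralatrexate dose differs from a missed one for DLT evaluability, and apply that definition identically at all sites. The same edit can remove the platelet overlap at exactly 25,000/µL. Which clinical rule to adopt is for the investigators. The cost is amendment wording and notice to the sites, with no added procedures or patients.

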5.5 Definition of Dose-Limiting Toxicity

The dose-limiting toxicity (DLT) observation period will be 2 cycles of therapy, from the start of Cycle 1 through the start of Cycle 3, including any delays (regardless of cause) to start of C3. It will be 42 days if there is no delay. If C3D1 is shorter than 42 days from C1D1, DLT will be evaluated through prior to administration of study therapy on C3D1.

Toxicities will be graded according to the National Cancer Institute Common Terminology Criteria for Adverse Events (CTCAE, Version 5.0) accessible at:

https://ctep.cancer.gov/protocolDevelopment/electronic_applications/ctc.htm#ctc_50

DLT will be defined as one of the following AEs that is **at least possibly related** to study treatment:

Hematologic

- Grade 4 neutropenia lasting > 7 days (despite the use of growth factor support).
- Grade 4 thrombocytopenia lasting > 7 days or requiring platelet transfusion.
- Grade 3 or 4 thrombocytopenia associated with grade 2 or higher bleeding.
- Grade 4 anemia not associated with lymphoma.
- Any Grade 5 AE.

Non-hematologic

- Grade \geq 3 pneumonitis without suspected infectious cause.
- Any \geq grade 3 AE that does not resolve to grade \leq 1 within 7 days with the exception of:
 - Grade \geq 3 asymptomatic laboratory abnormalities, including lipase or amylase, that do not require hospitalization or delay of treatment.
 - Grade 3 nausea or vomiting, that improves to grade \leq 2 within 7 days with supportive measures.
 - Grade 3 fatigue that improves to grade \leq 2 within 14 days with supportive measures.
 - Grade 3 asymptomatic endocrinopathy of any duration.
 - Grade 3 fatigue related to endocrinopathy that resolves within 7 days of hormone-replacement or corticosteroid therapy.
 - Grade 3 inflammatory response attributed to local antitumor response of any duration.
 - Vitiligo or alopecia of any grade and duration.
- Any Grade 5 AE

5.6 Definition of the MTD and Recommended Phase 2 Dose

Dose escalation will proceed according to the schema outlined in Table 5.3. The maximum tolerated dose (MTD) is defined as the highest dose level at which < 2 out of 6 evaluable subjects experienced DLT. The MTD will be considered the recommended phase 2 dose (RP2D), however the principal investigator may ultimately choose a lower dose level as the RP2D, depending on toxicity considerations, dose reduction on subsequent cycles, and other considerations.

